6.2. Treatment Assignment

Subjects will be assigned to study treatment in accordance with the randomization schedule generated by Clinical Statistics, prior to the start of the study, using validated internal software to receive **either**:

Mepolizumab:	or	Placebo (0.9% sodium chloride):
Three 100 mg SC injections administered every 4 weeks (8 administrations)		Three SC injections administered every 4 weeks (8 administrations)

Due to potential differences in standards of care between regions, the randomization will be stratified by region.

An unblinded site staff member will be assigned to the study to prepare the appropriate medication according to the study subject's treatment assignment. Subjects eligible to enter the study will be assigned to treatment randomly through an interactive response technology (IRT).

Subjects will be monitored during SC administration and for 1 hour after the first three administrations and then follow monitoring policies for the center. Such monitoring will include general safety monitoring including monitoring for both systemic reactions (e.g., hypersensitivity) and local site reactions. In the event of an acute severe reaction (e.g., anaphylaxis) following administration of study treatment, there are personnel/staff onsite at the treatment facility who are appropriately trained in basic life support to manage the subject including administration of medications (e.g., epinephrine), and have access to a system that can promptly transport the patient to another facility for additional care if appropriate.

6.3. Treatment Blinding

Once prepared mepolizumab and placebo will be identical in appearance and will be administered by a blinded member of the site staff. The blinding of those involved in the evaluation of the study, i.e., physician, nurse and subject will be maintained at all times.

This will be a double-blind study and the following will apply.

- The investigator or treating physician may unblind a subject's treatment assignment **only in the case of an emergency** OR in the event of a serious medical condition when knowledge of the study treatment is essential for the appropriate clinical management or welfare of the subject as judged by the investigator.
- Investigators have direct access to the subject's individual study treatment.
- It is preferred (but not required) that the investigator first contacts the GSK Medical Monitor or appropriate GSK study personnel to discuss options before unblinding the subject's treatment assignment.
- If GSK personnel are not contacted before the unblinding, the investigator must notify GSK as soon as possible after unblinding, but without revealing the treatment assignment of the unblinded subject, unless that information is important for the safety of subjects currently in the study.
- The date and reason for the unblinding must be fully documented in the CRF.

A subject will be withdrawn from study treatment if the subject's treatment code is unblinded by the investigator or treating physician. The primary reason for discontinuation of study treatment (the event or condition which led to the unblinding) will be recorded in the CRF (Section 5.4).

GSK's Global Clinical Safety and Pharmacovigilance (GCSP) staff may unblind the treatment assignment for any subject with an SAE. If the SAE requires that an expedited regulatory report be sent to one or more regulatory agencies, a copy of the report, identifying the subject's treatment assignment, may be sent to investigators in accordance with local regulations and/or GSK policy.

[figure not shown]
6.4. Blood Eosinophil Blinding

Investigators, GSK personnel involved in the study, and subjects will be blinded to the results of absolute blood eosinophil counts, total white blood cell counts, and white blood count differentials (%). Subjects that have an increase in blood eosinophils above the predetermined threshold will be instructed to take OCS capsules. In order to maintain the blind, this treatment will be with blinded OCS capsules.

All subjects will be provided 2 bottles of blinded OCS capsules, one containing 5mg OCS capsules (active OCS treatment) and a second one containing matching placebo capsules (placebo OCS treatment). These will be dispensed to each subject at each scheduled clinic visit and as needed. Subjects will also have blood drawn at each visit to assess the blood eosinophil count (Hematology assessment in Table 4).

A brief schematic of the trigger alert system is shown in Figure 3.

Figure 3 Blood eosinophil blinding and blinded OCS trigger schematic

Blood eosinophil-unblinded GSK personnel/delegates not involved with other aspects of study conduct will review the results from the central laboratory for absolute blood eosinophil count. If a pre-specified threshold blood eosinophil level (i.e., 2 x Baseline value [randomization] *or* Baseline value + 2500 cells/ μ L) is reached (eosinophilia flare), blood eosinophil-unblinded GSK personnel/delegates will communicate with the investigator to initiate blinded OCS treatment from one of the bottles provided (active treatment) unless the subject's HES therapy (OCS, cytotoxic agent, or immunosuppressive agent) has already been increased due to a symptom flare within the past 2 weeks. The subject will take the blinded OCS from the assigned bottle for ~2 weeks. A subject who does not reach the pre-specified blood eosinophil threshold with a similar blood draw date will be selected to initiate a placebo treatment in a blinded manner, to maintain study blood eosinophil blinding.

The dosing regimen for a course of blinded OCS is as shown in [Table 1](#).

Table 1 A course of blinded OCS regimen

Days	Dose (mg/day)	Number of 5mg capsules/day
1-3	40	8
4-6	20	4
7-9	10	2
10- Until notified regarding whether to discontinue or start a new course of blinded OCS regimen Otherwise, until the next scheduled clinic visit	5	1

Approximately 2 weeks after the scheduled clinic visit, the blood eosinophil count will be assessed again for the subject who started blinded OCS (both active and placebo). The subject who has taken active blinded OCS will be instructed to continue with a new course of blinded OCS regimen from Day 1 (i.e., 40mg) until the next scheduled clinic visit if the blood eosinophil count is at or above the threshold unless the subject's HES therapy (OCS, cytotoxic agent, or immunosuppressive agent) has been increased due to a symptom flare since the initiation of the current course of blinded OCS, and discontinue if the blood eosinophil count is below the threshold. For subjects taking placebo-blinded OCS, continuation/discontinuation of blinded OCS will be determined depending on the continuation/discontinuation of their matched subject on active-blinded OCS as described in [Figure 3](#).

A subject whose blood eosinophil count is at or above the threshold while receiving blinded placebo OCS will be re-evaluated when the subsequent test result from the scheduled clinical visit is available to determine whether blinded active OCS should be initiated.

A subject who starts blinded OCS based on the 2 weeks post-randomization (Visit 3) blood eosinophil count (both the active OCS and the matched placebo OCS subjects) will continue taking the blinded OCS until they return to the next scheduled clinic visit (Visit 4).

In the event that a subject has a blood eosinophil count that reaches the pre-defined threshold to trigger blinded active OCS for 2 consecutive monthly scheduled clinic visits, blood eosinophil-unblinded GSK physician/delegates will inform the investigator so that the investigator can take further measures as necessary.

Subjects who have to travel a great distance to the study site will be given an option to have a between-clinic visit blood draw locally and ship the sample to the central laboratory.

6.5. Packaging and Labeling

The contents of the label will be in accordance with all applicable regulatory requirements.

6.6. Preparation/Handling/Storage/Accountability

A description of the methods and materials required for preparation of mepolizumab or placebo will be detailed in the unblinded reference manual.

The investigator or designee must confirm appropriate temperature conditions have been maintained during transit for all study treatment received and any discrepancies are reported and resolved before use of the study treatment.

- Only subjects enrolled in the study may receive study treatment and only authorized site staff may supply or administer study treatment. All study treatments must be stored in a secure environmentally controlled and monitored (manual or automated) area in accordance with the labelled storage conditions with access limited to the investigator and authorized site staff.
- The investigator, institution, or the head of the medical institution (where applicable) is responsible for study treatment accountability, reconciliation, and record maintenance (i.e., receipt, reconciliation and final disposition records).
- Further guidance and information for final disposition of unused study treatment are provided in the Study Reference Manual (SRM).
- Under normal conditions of handling and administration, study treatment is not expected to pose significant safety risks to site staff. Take adequate precautions to avoid direct eye or skin contact and the generation of aerosols or mists. In the case of unintentional occupational exposure notify the monitor, GSK Medical Monitor and/or GSK study contact.
- A Material Safety Data Sheet (MSDS)/equivalent document describing occupational hazards and recommended handling precautions either will be provided to the investigator, where this is required by local laws, or is available upon request from GSK.

Mepolizumab must be stored in a secure area under the appropriate physical conditions for the product, which includes storage in a refrigerator or at a temperature of 2-8°C and protected from light. Maintenance of a temperature log (manual or automated) is required. Access to study treatment will be limited to the investigator's authorized unblinded site staff. Maintenance of a temperature log (manual or automated) is required. Study treatment must be dispensed or administered only to subjects enrolled in the study and in accordance with the protocol.

6.7. Compliance with Study Treatment Administration

Study treatment will be subcutaneously administered to subjects at the site. Administration will be documented in the source documents and reported in the CRF.

Compliance with blinded OCS will be based on pill counts at the time of dispense and collection of the bottles. These will be documented in the source documents and reported in the CRF.

6.8. Treatment of Study Treatment Overdose

The dose of mepolizumab considered to be an overdose has not been defined. There are no known antidotes and GSK does not recommend a specific treatment in the event of a suspected overdose. The investigator will use clinical judgment in treating the symptoms of a suspected overdose.

In the event that mepolizumab is administered more than as detailed in the protocol in terms of dose or frequency, the investigator should contact the GSK Medical Monitor immediately.

6.9. Treatment after the End of the Study

Subjects who complete the protocol-specified assessments for the 32-week period from randomization (Section 4.3) will be evaluated, and if eligible, may be enrolled into an extension study to receive open-label mepolizumab.

The investigator is responsible for ensuring that consideration has been given to the post-study care of the subject's medical condition, whether or not GSK is providing specific post-study treatment.

6.10. Concomitant Medications and Non-Drug Therapies

6.10.1. Permitted Medications and Non-Drug Therapies

Use of standard HES therapy including OCS, immunosuppressive or cytotoxic therapy (e.g., hydroxyurea, IFN α , cyclosporine, imatinib, methotrexate, azathioprine) will be permitted during the study. As specified in Inclusion Criterion #6, subjects must be on a stable dose of HES therapy for the 4 weeks prior to randomization (Visit 2) [Section 5.1]. The same regimen of HES therapy must be maintained throughout the 32-week study treatment period unless there is worsening of symptom(s) that requires an increase in therapy. If a subject has worsening of symptom(s) and requires an increase in therapy after randomization, the subject will be considered to be experiencing a flare (Section 7.3.1). Once the subject regains disease control, the investigator is encouraged, as medically appropriate, to adjust the dose of HES therapy back to the level prior to the disease worsening.

A reduction in standard HES therapy dose for safety reasons, with return to the original dosing regimen when possible, is permitted in consultation with the GSK Medical Monitor.

Additional therapies required to treat non-HES related medical conditions during the study are permitted in consultation with the GSK Medical Monitor and must be prospectively captured in the CRF.

6.10.2. Prohibited Medications and Non-Drug Therapies

Initiation of new medications or herbal remedies which may alter the course of HES or interact with the study treatment is prohibited within their specified timeframe and throughout the study (Visit 0 to Visit 11 inclusive) with the exception of HES therapy to treat an HES flare (Section 7.3.1).

In addition, the following medications will be prohibited:

- Any investigational agents (biologic or non-biologic) within the 30 days or 5 drug half-lives whichever is longer, prior to screening (Visit 1), and until Visit 11. The term “investigational” applies to any drug not approved for sale in the country in which it is being used or investigational formulations of marketed products.
- Any other biologic agents (except for IFN α): within 30 days or 5 half-lives, whichever is longer, of screening (Visit 1), and until Visit 11.

In the event that the use of a prohibited medication is identified by the study site, the investigator must use clinical judgment in balancing protocol compliance (discontinuing the medication) and subject safety. The investigator should assess whether the medication is required or likely to be required to maintain subject’s health in control. The investigator also should assess whether the medication can be stopped after subject’s health is re-established.

7. STUDY ASSESSMENTS AND PROCEDURES

Protocol waivers or exemptions are not allowed with the exception of immediate safety concerns. Therefore, adherence to the study design requirements, including those specified in the Time and Events Table, are essential and required for study conduct.

This section lists the procedures and parameters of each planned study assessment. The exact timing of each assessment is listed in the Time and Events Table (Section 7.1).

The following points must be noted:

- Subject-completed assessments are done at the beginning of a visit in Section 7.1 in the order presented in the electronic device.
- Blood draws are done after vital signs and prior to dosing of study treatment.
- The timing and number of planned study assessments, including safety, PK, and PD assessments may be altered during the course of the study based on newly available data to ensure appropriate monitoring.
- The institutional Review Board (IRB)/Independent Ethics Committee (IEC) and investigators will be informed of any safety issues that require alteration of the safety monitoring scheme or amendment of the Informed Consent Form.

7.1. Time and Events Table

Table 2 Time and Events Table

Procedures	Pre-screen	Screen	Randomization	Double-blinded treatment period												Additional follow-up	
				3	4	5	6	7	8	9	10	11 End-of-treatment	Flare ¹⁹	3-11 for subjects who prematurely discontinue study treatment ²⁰	EW		12
Study visit	0	1	2														
Study week		Up to ~4 weeks (wks)	0	2 (± 5 days)	4 ±1 wks	8 ±1 wks	12 ±1 wks	16 ±1 wks	20 ±1 wks	24 ±1 wks	28 ±1 wks	32 ±1 wks					~12 wks after last dose ±1 wks
Informed consent ¹	X																
Demography	X																
Medical history		X															
History of HES (diagnosis/flare) and treatment (past 12 months)	X																
CV history/risk factors		X															
Inclusion/exclusion		X	X														
Parasite screening ²		X															
Efficacy and PRO assessments																	
Subject-RTS ³					X	X	X	X	X	X	X	X					X
SSR ²			X		X	X	X	X	X	X	X	X	X				
Modified MSAS-SF ³			X		X	X		X		X		X	X				X
PROMIS sleep and physical function scales ²			X		X	X		X		X		X					
SF-36 v2 ³			X		X	X	X	X	X	X	X	X	X		X		
WPAI-GH v2 ³			X		X	X	X	X	X	X	X	X	X				X
Steroid perception questionnaire ³			X														
HES Core Assessments (clinician assessment) /Flare detail			X		X	X	X	X	X	X	X	X	X	X	X	X	
Clinician-RTS					X	X	X	X	X	X	X	X					X

Procedures	Pre-screen	Screen	Randomization	Double-blinded treatment period												Additional follow-up	
				3	4	5	6	7	8	9	10	11 End-of-treatment	Flare ¹⁹	3-11 for subjects who prematurely discontinue study treatment ²⁰	EW		
Study visit	0	1	2														
Study week		Up to ~4 weeks (wks)	0	2 (± 5 days)	4 ±1 wks	8 ±1 wks	12 ±1 wks	16 ±1 wks	20 ±1 wks	24 ±1 wks	28 ±1 wks	32 ±1 wks					~12 wks after last dose ±1 wks
HCRU			X		X	X	X	X	X	X	X	X				X	
Spirometry			X			X		X		X		X	X				
Echocardiogram ⁴		X										X	X				
Safety assessments																	
Physical examination ⁵		X	X		X	X	X	X	X	X	X	X	X				
Height and weight ⁶		X	X					X				X				X	
Concomitant meds including maintenance OCS	X	X	X	X	X	X	X	X	X	X	X	X	X	X	X	X	
Vital signs ⁷		X	X		X	X	X	X	X	X	X	X	X			X	
ECG		X										X	X				
AEs			X	X	X	X	X	X	X	X	X	X	X	X	X	X	X
SAEs		X	X	X	X	X	X	X	X	X	X	X	X	X	X	X	X
Laboratory assessments⁸																	
Hematology ⁹		X	X	X	X	X	X	X	X	X	X	X	X	X	X	X ²¹	
Chemistry ¹⁰		X			X	X	X	X	X	X	X	X	X	X	X ²¹	X ²¹	
Troponin		X			X	X	X	X	X	X	X	X	X	X ²¹	X ²¹	X ²¹	
Pregnancy test ¹¹		X	X		X	X	X	X	X	X	X	X		X ²¹	X ²¹		
Aldolase		X			X	X	X	X	X	X	X	X	X				
Lipoproteins (fasting) ¹²		X															
Urinalysis ¹³		X										X		X ²¹	X ²¹		
Hep B & C serology ¹⁴		X															
F/P status ¹⁵		X															
T-cell profile		X										X		X ²¹	X ²¹		
Total IgE			X														

Procedures	Pre-screen	Screen	Randomization	Double-blinded treatment period												Additional follow-up	
				3	4	5	6	7	8	9	10	11 End-of-treatment	Flare ¹⁹	3-11 for subjects who prematurely discontinue study treatment ²⁰	EW		
Study visit	0	1	2														
Study week		Up to ~4 weeks (wks)	0	2 (± 5 days)	4 ±1 wks	8 ±1 wks	12 ±1 wks	16 ±1 wks	20 ±1 wks	24 ±1 wks	28 ±1 wks	32 ±1 wks					~12 wks after last dose ±1 wks
PK					X			X				X		X ²¹	X ²¹	X ²¹	
PD (IL-5)			X									X	X				
Immunogenicity (Anti-drug antibody)			X					X				X		X ²¹	X ²¹	X ²¹	
Genetics ¹⁶			X														
Sample collection for biomarker sub-study ¹⁷			X									X	X	X ²¹	X ²¹		
Investigational product & other study treatment																	
Study treatment administration ¹⁸			X		X	X	X	X	X	X	X						
Dispense/collect blinded OCS			X	X	X	X	X	X	X	X	X	X		X	X		
Interactive Response Technology (IRT)/electronic CRF (eCRF)/electronic Diary (eDiary)																	
Register visit on IRT	X	X	X	X	X	X	X	X	X	X	X	X	X	X	X	X	X
Complete eCRF		X	X	X	X	X	X	X	X	X	X	X	X	X	X	X	X
Dispense (D) /collect (C) eDiary ²²		D										C		C for Visit 11	C		
Review eDiary			X	X	X	X	X	X	X	X	X	X		X	X		

EW: Early withdrawal

1. Pre-screen visit to obtain informed consent can occur on the same day as Visit 1, but informed consent must be obtained prior to starting Visit 1 procedures.
2. Parasitic screening is only required in countries with high-risk or for subjects who have visited high-risk countries in the past 6 months. Sites should use local laboratories.
3. Subject-completed assessments are done at the beginning of a visit.
4. Echocardiogram is performed to support CV assessment at screening and at the end of study treatment for all subjects. Echocardiogram at Visit 1 is required unless there is a documented result within the previous 6 months from Visit 1.
5. Findings during physical examination related to HES will be recorded in the HES Core Assessments/flare detail.
6. Height to be measured at screening only.
7. Vital sign measurements will include temperature, systolic and diastolic blood pressure and pulse rate.
8. During the treatment period, all laboratory samples (Table 4) should be obtained **pre-dose**.
9. Refer to Section 6.4 for additional blood draw between the scheduled clinical visits for subjects who will administer blinded OCS.
10. Clinical chemistry will include analytes and liver chemistry monitoring.
11. Negative urine pregnancy test result must be confirmed prior to dosing in women of reproductive potential.
12. Lipoprotein (fasting) included in clinical chemistry. Subject must be in a fasting state. If the subject has not fasted, he/she may return to the clinic to collect this sample.
13. Urine tests are done using dipstick. If found abnormal, the urine sample will be sent to the central laboratory for further testing.
14. If test was performed within 3 months prior to randomization, testing at screening is not required.
15. F/P test is required if no documented results are available.
16. Informed consent for optional sub-studies (e.g., genetics research) must be obtained before collecting a sample. Genetic sample collection is recommended at Visit 2, but may be drawn at any time after the subject is consented and randomized.
17. Sample collection for the optional biomarker sub-study should be done after obtaining a written consent.
18. The date and time of the administration of study treatment will be recorded in the CRF. For safety monitoring requirement, refer to Section 6.2.
19. Assessments will be collected when possible depending on the clinical status during worsening of symptoms between scheduled clinic visits to evaluate for an HES flare. Spirometry for a respiratory flare, and troponin, echocardiogram, & ECG for a CV flare will be performed (Selective assessments depending on the type of flare are noted in the table with the gray shade). Echocardiogram will be performed only if there is a change in HF classification (see Section 12.7) and/or the investigator determines that there is a need for assessment. When attending the clinic visit at the time of a suspected HES flare is not possible, the investigator should make every effort to evaluate the subject via telephone and complete the HES Core Assessments (Section 7.3.2).
20. Subjects who prematurely discontinue study treatment will continue to attend 4-weekly scheduled clinic visit and complete these assessments. Blood samples for hematology will be collected at these visits for blinded blood eosinophil monitoring (Section 6.4). All other laboratory assessments are completed at 4 and 12 weeks after the last dose only as noted in footnote #21.
21. Approximately 4 weeks after the last dose of study treatment, every attempt should be made to collect urine and blood samples for laboratory assessments. In addition, all subjects will be brought in for an additional follow-up visit 12 weeks after the last dose, including the collection of a blood sample for measurement of anti-drug antibodies and PK, unless the subject receives open-label mepolizumab according to the protocol criteria at that time.
22. Subjects will complete BFI and HES daily symptoms (HES-DS) in the eDiary on a daily basis. Subjects must complete the eDiary for at least 7 days prior to randomization. Subjects who prematurely discontinue study treatment will continue daily eDiary completion and return the eDiary at Visit 11 for EW.

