5.4. Withdrawal/Stopping Criteria

A subject may withdraw from study treatment at any time at his/her own request, or may be withdrawn at any time at the discretion of the investigator for safety, behavioural or administrative reasons. If a subject withdraws from the study, he/she may request destruction of any samples taken, and the investigator must document this in the site study records.

Withdrawal from study treatment

Subjects who discontinue study treatment prematurely (for any reason) should, where possible, continue in the study per protocol (Refer to Section 7.1 – Visits 3-11 for subjects who prematurely discontinue study treatment) until 32 weeks after randomization, including the collection of biological samples for laboratory assessments approximately 4 weeks and 12 weeks after the last dose of study treatment as well as daily eDiary completion. Subjects will be considered to receive open-label mepolizumab after 32 weeks lapse from randomization, completing ‘Visit 11 for subjects who prematurely discontinue study treatment’ (Section 4.1). If a subject’s last dose of study treatment was on Visit 9 (Week 24) and the subject does not continue with open-label mepolizumab after completing Visit 11 assessments (32 weeks from randomization), there will be an additional 8-week follow-up period, concluding with the 12 weeks post-last dose follow-up visit (Visit 12).

Reasons for premature discontinuation of study treatment must be captured in the CRF, e.g., AE, lack of efficacy, protocol deviation, pregnancy, investigator discretion, consent withdrawal, lost to follow-up, study termination.

If a subject experiences an organ-threatening or a life-threatening event, the investigator should discuss study treatment continuation with the GSK Medical Monitor.

Subjects will be withdrawn from study treatment for any of the following reasons:

- Meet the **liver chemistry stopping criteria** (Section 5.4.1)
- Meet **QTc stopping criteria** (Section 5.4.2)

- Use **prohibited medication** (i.e., as noted in Exclusion Criteria # 13, 14, & 15, and Section 6.10.2, Prohibited Medications and Non-Drug Therapies) that cannot be safely discontinued while maintaining the subject's health.

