#### 7.6.7.2. Strategy for Intercurrent (Post-Randomization) Events

The treatment effect to be estimated (estimand) will be the ‘treatment policy’ effect of initial randomised treatment. A treatment policy strategy will be used for the intercurrent events of a) discontinuation of study medication and b) receipt of alternative HES medications. Subjects with missing SSR score at Week 32 will be included in the analysis with the largest (i.e. worst) value observed for any subject.

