**7.6.9.2. Strategy for Intercurrent (Post-Randomization) Events**

The treatment effect to be estimated (estimand) will be the ‘treatment policy’ effect of initial randomised treatment. A treatment policy strategy will be used for the intercurrent events of a) discontinuation of study medication and b) receipt of alternative HES medications. Subjects with missing change from baseline PROMIS score at Week 32 will be included in the analysis with the largest (i.e. worst) value observed for any subject.

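### PROMIS, SSR and FEV1/FVC are assigned a treatment-policy strategy for stopping study drug, but the visit schedule does not call for these measures once a subject has stopped

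*Protocol*

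**What the plan says.** SAP 7.6.2.2 (FEV1/FVC), 7.6.7.2 (SSR) and 7.6.9.2 (PROMIS) use the same sentence: "A treatment policy strategy will be used for the intercurrent events of a) discontinuation of study medication and b) receipt of alternative HES medications". The missing-data rules differ. For PROMIS, subjects with a "missing change from baseline PROMIS score at Week 32 will be included in the analysis with the largest (i.e. worst) value". For SSR, "Subjects with missing SSR score at Week 32 will be included in the analysis with the largest (i.e. worst) value observed for any subject". For FEV1 and FVC nothing is imputed; SAP 7.6.2.2 and 7.6.2.3 specify a repeated-measures mixed model under missing at random.

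The protocol sends subjects who stop study treatment to a separate column of the schedule. Section 5.4 says "Refer to Section 7.1 – Visits 3-11 for subjects who prematurely discontinue study treatment", and footnote 20 to Table 2 says "Subjects who prematurely discontinue study treatment will continue to attend 4-weekly scheduled clinic visit and complete these assessments". Diary measures are covered separately by footnote 22: "Subjects who prematurely discontinue study treatment will continue daily eDiary completion and return the eDiary at Visit 11 for EW".

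**The concern.** A treatment-policy strategy needs the outcome measured after the subject has stopped the drug. If the schedule does not ask for it, every discontinuer's Week 32 value is missing, however faithfully that subject attends. The missing-data rule then decides how discontinuation enters the comparison. The result would carry a treatment-policy label while answering a different question.

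Two things are at stake. The reported effect may be misread. For PROMIS and SSR, values that could have been measured are also replaced by extreme ranks. That costs power, and it shifts the comparison if more subjects stop in one arm than in the other.

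**Working it through.** **Step 1: the schedule.** Marks read by column position in Protocol Table 2:

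| Row | Marked at | Discontinuer column |
|---|---|---|
| "PROMIS sleep and physical function scales" | Visits 2, 4, 5, 7, 9, 11 | none |
| SSR | Visits 2, 4 to 11, Flare | none |
| Spirometry | Visits 2, 5, 7, 9, 11, Flare | none |
| HES Core Assessments (control) | includes the discontinuer column | marked |
| Blinded OCS dispensing (control) | includes the discontinuer column | marked |

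The two control rows show that the column can be located by this count. The SAP file holds two versions of the plan, and its two copies of the schedule agree for the three measures.

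**Step 2: can any other value reach the analysis?** For PROMIS, no: it is not marked at the Flare visit. For SSR and spirometry, sometimes. Footnote 19 says "Spirometry for a respiratory flare, and troponin, echocardiogram, & ECG for a CV flare will be performed", and SSR is also marked under Flare. The SAP reporting standards (16.5.2 in the amended version) move unscheduled data to the nearest scheduled visit if that visit is empty. A Flare value near Week 32 could therefore stand in, but only for subjects who are worsening.

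**Step 3: what the analysis then estimates.**
- PROMIS and SSR: stopping the drug is scored as the worst outcome seen, which is how a composite strategy behaves.
- FEV1/FVC: the model borrows from subjects still being measured, nearly all of them on treatment, which leans towards the outcome had the subject stayed on drug.
- Safeguards: PROMIS has a supportive mixed model (SAP 7.6.9.3), also under missing at random. SSR has no sensitivity analysis (SAP 7.6.7.3).

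**Step 4: how many subjects.** The documents give no discontinuation rate. At an assumed 5%, 10% or 20% of 40 per arm, 40 × 0.05 = 2, 40 × 0.10 = 4 and 40 × 0.20 = 8 subjects per arm would have no scheduled Week 32 value.

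**Step 5: illustration for a worst-value outcome.** There is no figure in the plan to reproduce. Assumed inputs: 40 per arm; continuous score; difference 1.4, SD 2.2 (1.4 / 2.2 = 0.64 SD); unstratified Wilcoxon test at two-sided 5%; discontinuation at random; missing values replaced by the worst observed value. The comparator is what the fix would deliver: off-treatment values observed, with the drug effect lost. Ranges span repeated runs.

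| Discontinuing per arm | Off-treatment values observed | Worst value substituted | Loss (points) |
|---|---|---|---|
| 5% | 74–75% | 69–70% | about 4–6 |
| 10% | 69–70% | 59–61% | about 9–10 |
| 20% | 57–58% | 42% | about 15–16 |

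With no true effect, type I error is about 6–7% at 10% v 5% missing and 11–12% at 15% v 5%. With fixed counts of 6 v 2 subjects out of 40 it is about 8%.

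**The case against.** **Worst-value substitution is a missing-data rule and leaves the estimand as stated.** That would be fair if a few discontinuers happened to miss Week 32. Here the value is unscheduled for all of them, so the rule alone fixes what discontinuation contributes.

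**The extracted tables are unreliable.** This stands in part. The SF-36 row differs between copies, one SAP copy shows a dosing mark at Visit 11 although the last dose is at Week 28, and the grey shading named in footnote 19 is lost. Section 5.4 also says discontinuers continue per protocol before it points to the column. Agreement across three copies makes an artefact unlikely for these rows, but the PDF should be checked.

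**The endpoints are exploratory.** This stands. All three lie outside the testing hierarchy in SAP 5.5. Flares and BFI item 3 are collected after discontinuation.

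Four stronger readings are tempting, and the documents do not support them:
- That all three outcomes are imputed. Spirometry is not.
- That discontinuers' outcomes can never be observed. That is strict for PROMIS only.
- That 10% discontinuation cuts power from 78% to 59%. The 78% assumes discontinuers keep the full drug effect, which collecting their data would not restore.
- That the inflated type I error threatens the trial's confirmatory claims. It does not reach them.

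**Conclusion.** The mismatch is real. Followed exactly, the plan does not deliver the treatment-policy effect it names for PROMIS, SSR and FEV1/FVC, because it schedules no post-discontinuation values for them. It should be corrected, but it does not affect the primary or secondary conclusions.

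The size depends on a discontinuation rate the documents do not give. For a worst-value outcome the power cost ranges from about 4–6 points at 5% per arm to about 15–16 points at 20%, and type I error rises when the arms lose unequal numbers. The effect size, SD and random discontinuation are also assumptions. The illustration suits a continuous score better than the five-category SSR and says nothing about spirometry.

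It also needs care for PROMIS physical function. The notes to SAP Tables 2.53 to 2.55 score 5 as no difficulty, so the largest change would be the best one. That is a separate error, to be settled before the worst-value rule is applied to that scale.

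**What to change.** Mark PROMIS and SSR, and spirometry where feasible, in the discontinuer column at visits where they are already scheduled, at minimum Week 32. Check RTS and MSAS-SF against the original PDF for the same gap. They share the strategy and the worst-value rule (SAP 7.6.6.2 and 7.6.8.2) and also appear unmarked, but their late marks are shifted in the extracted table.

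If collection can no longer change, relabel the strategy for discontinuation in SAP 7.6 as composite for PROMIS and SSR and as hypothetical for spirometry.

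The first option costs a few minutes at visits subjects already attend. The second costs wording only.
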